### 4.4 Clinical Efficacy

### 4.4.1 Subject Evaluation & Statistics

The FAS will be the basis for the evaluation of clinical efficacy.

Disease assessment will be performed at the end of Cycles 1, 3, and thereafter every 2-3 cycles at the discretion of the treating physician. While the bone marrow aspirate/biopsy will be performed as clinically indicated, testing will occur at least once every 3 cycles.

Descriptive statistics will be provided for continuous variables and frequency tables will be used to summarize categorical variables. The Overall Response Rate and the proportions of subjects who experienced CR, Cri, PR, MLFS (morphologic leukemia-free state), hematologic improvements, Recurrence of Disease (RD) and Best Response measurement along with the corresponding exact 95% confidence intervals will be displayed.

Kaplan-Meier method will be used to estimate the duration of response, progression-free survival and overall survival. These time to event variables will be summarized using the 25th percentile, Median, and 75th percentile as well as the minimum and maximum time to event, calculated by Kaplan-Meier method, and will be displayed graphically.

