### Study Objectives & Endpoints

Primary Objectives	Safety & Tolerability
	Determine Dose Limiting Toxicities
	Establish MTD and RP2D
Secondary Objectives	IACS-010759 pharmacokinetics and food effect
	Preliminary Clinical Efficacy (overall response rates, duration of
	response, progression-free survival, overall survival)
Exploratory objectives	Pharmacodynamic and exploratory biomarkers of activity of IACS-
	010759

Clinical study data will be entered into Medidata Rave, the clinical data base, via electronic case report forms. The Statistical Analysis Plan (SAP) will include detailed and specific description of all analysis to be performed on the clinical data from this study. The SAP will be finalized prior to database lock.

All statistical analyses will be performed using Version 9.4 or later of Statistical Analysis Software (SAS®). Data summaries will use descriptive statistics (number of subjects [n], mean, standard deviation [SD], Q1, median, Q3, minimum, and maximum) for continuous variables, and frequency and percentage for categorical and ordinal variables. If there are missing values, the number missing will be presented, but without a percentage. All data collected will be included in by-subject data listings.

Unless otherwise specified, all tests will be two-tailed using a 0.05 level of significance. All confidence intervals (CIs) will be two-sided 95% confidence intervals.

All subjects who received any study drug and who had any on-treatment evaluation will be included in the Full Analysis Set (FAS).

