#### Hematologic Improvement (HI):

Hematologic response must be described by the number of positively affected cell lines.

- Erythroid response (E) (pretreatment Hgb <11 g/dL)

- Hgb increase by ≥1.5 g/dL
- Platelet response (P) (pretreatment platelets <100 x10^9/L)
- Absolute increase of  $\ge 30 \times 10^9$ /L for subjects starting with  $> 20 \times 10^9$ /L platelets
- $\circ$  Increase from < 20 x 10^9/L to > 20 x 10^9/L and by at least 100%
- Neutrophil response (N) (pretreatment ANC <1.0 x10^9/L)
- o At least 100% increase and an absolute increase > 0.5 x 10^9/L
- Blast response (B)≥50% reduction in peripheral blood or bone marrow blasts but still >5%

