### • Recurrence of Disease (RD)

Relapse after CR is defined as a reappearance of leukemic blasts in the peripheral blood or  $\geq 5\%$  blasts in the bone marrow aspirate not attributable to any other cause or reappearance or new appearance of extramedullary leukemia. Relapse after PR is similarly defined with reappearance of significant numbers of peripheral blasts and an increase in the percentage of blasts in the bone marrow aspirate to > 25% not attributable to any other cause or reappearance or new appearance of extramedullary leukemia.

Best Response measurement: Response will be measured and defined for primary endpoints as the best response achieved during the first 3 cycles of therapy, or at time off study, for those subjects discontinuing treatment before the completion of 3 cycles of therapy. Best response is defined to be the best-measured response (ORR=CR+CRp+PR+MLFS) post-treatment up to that time. Best response will also be evaluated for the full treatment period using all assessments up to and including treatment discontinuation.

**Duration of Response**: length of time from the first objective evidence of response to the first objective evidence of disease progression.

**Progression-Free Survival**: length of time (up to 5 years) from the date of first treatment to the first objective evidence of disease progression or death, whichever is earlier.

**Overall Survival**: length of time from the date of first administration of study drug to the date of death from any cause.

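### The only stated basis for the recurrence-of-disease proportion is the full analysis set, yet only subjects with a CR or PR can have a recurrence, so the figure understates relapse among responders

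*Combined protocol and SAP*

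**What the plan says.** Section 4.4.1 sets one analysis set for efficacy: "The FAS will be the basis for the evaluation of clinical efficacy". Under Study Objectives & Endpoints, a subject enters the FAS by being treated and having at least one on-treatment evaluation. Response and baseline blood counts play no part.

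The same section lists the summaries to be given as proportions of subjects. After ORR, CR, CRi, PR and MLFS come "hematologic improvements, Recurrence of Disease (RD) and Best Response measurement along with the corresponding exact 95% confidence intervals will be displayed". It also plans Kaplan-Meier estimates of duration of response.

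Section 4.4.2 defines RD for two groups only: "Relapse after CR is defined as a reappearance of leukemic blasts in the peripheral blood" (with marrow and extramedullary alternatives), and "Relapse after PR is similarly defined with reappearance of significant numbers of peripheral blasts" together with a rise in marrow blasts. Nothing is said about relapse after CRi or MLFS, although both count towards ORR.

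Hematologic improvement (HI) has four categories. Three carry a pretreatment condition: hemoglobin below 11 g/dL for erythroid, platelets below 100 x 10^9/L for platelet, and ANC below 1.0 x 10^9/L for neutrophil response. The fourth, blast response, carries none.

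**The concern.** A subject who never reached CR or PR cannot have RD as defined, but under the general FAS rule still counts in its denominator. The resulting figure mixes two quantities: how often subjects respond, and how often responders relapse. It moves in a misleading direction, because a drug with few responses that are soon lost would show a low recurrence proportion. The exact interval around it would be an interval for responding and then relapsing, not for the risk of relapse after response. A crude proportion also ignores that responders are followed for different lengths of time.

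A weaker form of the same issue affects three HI lineages. A subject above the pretreatment threshold for a lineage cannot meet that lineage's criterion, but would be counted in its denominator.

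**Working it through.** The plan states no RD or HI figure and no efficacy sample size calculation, so there is no number of its own to reproduce. The check compares two denominators. All intervals are exact (Clopper-Pearson), two-sided 95%.

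**Inputs from the document.**
- Maximum enrolment is 48 (synopsis; 36 in escalation + 12 additional in expansion). The FAS could be smaller.
- The expansion phase has 18 subjects (4.1.5).
- Background response rates of 10% to 30% in relapsed AML (2.1) are used only as an illustrative range.

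**Assumed inputs.** Numbers of responders, relapses and HI-eligible subjects. All responders in the RD examples are taken to be CR or PR.

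**Recurrence of disease.** Because every RD subject is a responder,

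RD / FAS = (responders / FAS) x (RD / responders).

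So RD/FAS cannot exceed the response share, and the ratio of the two proportions is 1 / (response share): 1/0.10 = 10 and 1/0.30 = 3.3. If every responder relapsed, 48 subjects would show 5/48 = 10.4% or 14/48 = 29.2%, where the proportion among responders is 100%.

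| N | Responders | Relapses | Over FAS (95% CI) | Over responders (95% CI) |
|---|---|---|---|---|
| 48 | 5 | 2 | 4.2% (0.5-14.3) | 40.0% (5.3-85.3) |
| 48 | 8 | 6 | 12.5% (4.7-25.2) | 75.0% (34.9-96.8) |
| 48 | 10 | 5 | 10.4% (3.5-22.7) | 50.0% (18.7-81.3) |
| 48 | 14 | 7 | 14.6% (6.1-27.8) | 50.0% (23.0-77.0) |
| 18 | 4 | 2 | 11.1% (1.4-34.7) | 50.0% (6.8-93.2) |

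With 8 responders and 6 relapses the intervals do not overlap: the upper FAS limit of 25.2% lies below the lower responder limit of 34.9%. The widths are 25.2 - 4.7 = 20.5 and 96.8 - 34.9 = 61.9 percentage points. The narrower interval carries no more information about relapse, since only the 8 responders can supply any.

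**HI, one lineage with a threshold, N = 48.** The ratio is 1 / (eligible share).

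| Eligible | Improved | Over FAS | Over eligible | Ratio |
|---|---|---|---|---|
| 43 | 9 | 18.8% | 20.9% | 48/43 = 1.1 |
| 34 | 7 | 14.6% | 20.6% | 48/34 = 1.4 |
| 24 | 5 | 10.4% | 20.8% | 48/24 = 2.0 |

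If all 48 are eligible there is no difference. The eligible share is not given. Section 7.2.2 expects most subjects to have neutropenia, thrombocytopenia or both at entry, which suggests a ratio near the low end for platelets and neutrophils.

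**The case against.** **The FAS denominator is inferred.** Section 4.4.1 gives the FAS as a general basis and does not attach it to RD or HI by name. An analysis set can contain an at-risk subset: duration of response sits under the same rule and can only be computed in responders. Full analysis detail is deferred to a SAP due before database lock. This stands as a caution, and a reader should not infer that the plan expressly fixes FAS denominators for RD and HI. But the FAS is the only basis offered. Elsewhere the protocol does narrow its population where it means to: evaluability for MTD (4.1.13), plasma levels (4.5.1) and biological activity (4.6.1).

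**Other outputs limit the harm.** ORR, CR, CRi and PR appear in the same display, and Kaplan-Meier duration of response deals with timing and unequal follow-up. Labelled as a share of all treated subjects, an FAS proportion is also correct. This lessens the consequence, but RD remains a separately planned proportion with its own interval.

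**HI as a whole is not shown to be understated.** A reader might infer that only subjects below a threshold can improve. Blast response has no such threshold, so a subject with adequate counts can still have HI, and an any-line HI proportion need not be too low. It would also go too far to say that HI rates follow the baseline mix and not the drug effect: an FAS rate still moves with drug effect, and section 4.4.1 plans no HI comparison between cohorts.

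**Any response is the wrong replacement denominator.** It would bring in CRi and MLFS subjects, for whom section 4.4.2 gives no relapse rule. This stands and shapes the fix.

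**Conclusion.** The point holds for RD. On the plan's only stated basis, the RD proportion is capped by the share of subjects with CR or PR and understates relapse among responders, by a factor of about 3.3 to 10 if 10-30% respond. That range rests on a background rate used as an assumption; the counts in the examples are also assumed. The algebra behind the cap needs no assumption beyond the FAS denominator and the RD definition.

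For HI the point is secondary. It applies to the erythroid, platelet and neutrophil lineages only, and is probably modest given the expected cytopenias at entry.

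A reader might infer a wider flaw in the trial's conclusions; the documents do not support that. RD and HI are descriptive summaries under a secondary objective of preliminary efficacy, and they feed neither the sample size, nor the DLT rules, nor the stopping boundaries. The correction is still worth making, because it changes a reported result and its interval.

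**What to change.** In section 4.4.1 or the SAP:

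1. Report RD as n/N with an exact interval among subjects who achieved a response for which relapse is defined. On the current text this is CR or PR. State whether CRi and MLFS count and, if they do, give the relapse definition that applies to them.
2. Present the timing of relapse through the Kaplan-Meier duration of response already planned.
3. If the FAS-based RD figure is kept, label it as a share of all treated subjects in the FAS.
4. Report erythroid, platelet and neutrophil improvement each as n/N among subjects meeting that lineage's pretreatment threshold. Blast response needs no such restriction, and any-line HI may stay on the FAS.

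The cost is wording only, with no new data or visits. Intervals will be wider and the relapse figure less favourable.

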#### 4.4.2 Endpoints & Assessment Methods

Objective Overall Response Rate (ORR) for subjects with AML include CR, CRi, PR and morphologic leukemia-free state [22] with or without cytogenetic response and hematologic improvements. The responses are defined as below:

### Complete Remission (CR)

For subjects to be classified as being in CR, they must have bone marrow regenerating normal hematopoietic cells and achieve a morphologic leukemia-free state and must have an ANC >  $1 \times 10^9$ /L and platelet count  $\ge 100 \times 10^9$ /L, and normal marrow differential with < 5% blasts, and subjects will be red blood cell (RBC) and platelet transfusion independent (defined as 4 weeks without RBC transfusion and 1 week without platelet transfusion). There should be no evidence of extramedullary leukemia.

Complete Remission with Incomplete Hematological Recovery (CRi)
 For subjects to be classified as being in CRi, they must fulfill the criteria for CR except for incomplete hematological recovery with residual neutropenia (ANC ≤ 1 × 10^9/L) with or without thrombocytopenia (platelet count < 100 × 10^9/L). In addition, subjects do not need to be RBC or platelet transfusion independent (modification to Cheson criteria).

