#### 4.1.9.3 *Intra-Subject Dose Escalation*

Intra-subject dose escalation of IACS-010759 (in accordance with the dosing schema in Table 1 and 2) will be permitted provided:

- Subject has completed ≥2 cycles at their current dose level and has not achieved a CR or Cri
- Subject has not experienced any grade 3 or higher non-hematologic drug-related toxicity, and

Subject has not experienced DLT,

- The dose may be escalated by one dose level no more frequently than every 2 cycles.
- The escalated dose level must have been fully evaluated and shown not to exceed the MTD (0 DLT of 3 or ≤1 DLT of 6)

If an intra-subject dose escalation occurs, laboratory monitoring will be increased to weekly during the first cycle of the increase dose.

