### 6 Study Drug

### 6.1 Study Drug Administration

Cohorts 1 and 2: For each cycle 1, a single oral dose of IACS-010759 will be administered on day 1. The next dose of IAC-010759 will be administered on day 8, and daily continuously for the duration of the study with no interruptions unless there are adverse events as described in Section 4.1.9. IACS-010759 doses will be separated by intervals of approximately 24 hours (+/- 3 hours).

Cohorts 3-6 and Dose Expansion: Based on the observed accumulation of IACS-010759 throughout the dosing period in cohorts 1 and 2, a modified dosing regimen is being implemented, consisting of an induction phase in which IACS-010759 is administered daily for up to 7 days, followed by a maintenance phase in which a lower dose is administered weekly (or as otherwise specified by the SMC based on safety, PK and PD data observed) to maintain steady state plasma levels. Dosing will proceed on this schedule for the duration of the study with no interruptions unless there are adverse events as described in Section 4.1.9.

IACS-010759 will be administered without food, at least 1 hour before and at least 2 hours after eating. Each dose of IACS-010759 should be administered with 8 ounces of water. If a dose is missed, the next dose will not be increased to account for missing a dose. The subject will take the next regular dose at the scheduled time. Following cycle 1 (28-day cycle for cohorts 1 and 2, 21 day cycle for subsequent cohorts), subjects will receive one cycle of therapy every 21 days (+/- 4 days).

In cohorts 1 and 2, treatment was administered as an inpatient for 24 hours on day 1 and then starting on day 8 for the next 7 days for all enrolled subjects. In cohorts 3 and 4, treatment will be administered as an inpatient for 24 hours on Day 7 of Cycle 1 for all enrolled subjects. In subsequent cohorts, treatment will be administered as an inpatient for 24 hours on Day 5 of Cycle 1 for all enrolled subjects. IACS-010759 will be self-administered and subjects instructed not to dose on days when PK/PD samples are collected until advised by the research staff. Self-administration can occur on days without PK/PD and subjects will record administration in a provided diary.

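### As worded, CRi requires residual neutropenia, so a subject with ANC >1 who was recently transfused or has isolated thrombocytopenia is scored MLFS, while an otherwise identical neutropenic subject is scored CRi

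*Combined protocol and SAP*

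**What the plan says.** All the response definitions are in section 4.4.2.

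- **CR** needs a regenerating marrow with a normal differential and <5% blasts, ANC >1 ×10⁹/L, platelets ≥100 ×10⁹/L, no extramedullary leukemia, and transfusion independence, "defined as 4 weeks without RBC transfusion and 1 week without platelet transfusion".
- **CRi**: "they must fulfill the criteria for CR except for incomplete hematological recovery with residual neutropenia", meaning ANC ≤1 ×10⁹/L. Platelets <100 ×10⁹/L may or may not be present as well. The paragraph then adds: "In addition, subjects do not need to be RBC or platelet transfusion independent (modification to Cheson criteria").
- **PR** needs total marrow blasts between 5% and 25%.
- **MLFS** needs only ≤5% marrow myeloblasts. It carries no count or transfusion condition.

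The opening of 4.4.2 builds ORR from CR, CRi, PR and MLFS. The Best Response paragraph later in the same section writes the formula as CR + CRp + PR + MLFS. CRp is defined neither there nor in the abbreviation list (9.2), and CRi is missing from that formula.

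Section 4.4.1 reports CR, CRi and MLFS as separate proportions with exact 95% confidence intervals. On timing it says: "Disease assessment will be performed at the end of Cycles 1, 3, and thereafter every 2-3 cycles at the discretion of the treating physician". Section 4.1.9.3 permits intra-subject dose escalation on several conditions, one being that the subject "has not achieved a CR or Cri".

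**The concern.** CRi would normally hold remissions that fall short of CR only on blood recovery. As written it holds only those that fall short on neutrophils. Subjects who fall short on platelets alone, or only because of a recent transfusion, have no remission category and drop to MLFS. The ordering is then inverted, since a subject with the same marrow, platelets and transfusion history but a lower ANC is placed higher.

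The CRi and MLFS proportions are both planned outputs, so the inversion goes straight into the efficacy tables. The CR/CRi status also feeds a condition in 4.1.9.3, so the wording reaches beyond the tables.

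**Working it through.** **Step 1: inputs.** The definitions are those of 4.4.2 set out above. Hold fixed a regenerating marrow with a normal differential, <5% blasts and no extramedullary leukemia. PR is then excluded, because it needs at least 5% blasts, and MLFS is always met.

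**Step 2: classify every combination of ANC, platelets and transfusion independence (TI).** The literal column takes CRi as requiring ANC ≤1, with TI waived. The last column reads the sentence beginning *In addition* as a second exception that stands on its own.

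| ANC (×10⁹/L) | Platelets (×10⁹/L) | TI | Literal reading | Separate-waiver reading |
|---|---|---|---|---|
| >1 | ≥100 | yes | CR | CR |
| >1 | ≥100 | no | **MLFS** | CRi |
| >1 | <100 | yes | **MLFS** | **MLFS** |
| >1 | <100 | no | **MLFS** | **MLFS** |
| ≤1 | ≥100 | yes | CRi | CRi |
| ≤1 | ≥100 | no | CRi | CRi |
| ≤1 | <100 | yes | CRi | CRi |
| ≤1 | <100 | no | CRi | CRi |

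Read literally, three of the four rows with ANC >1 have no remission category, while every row with ANC ≤1 has one. The separate-waiver reading repairs only the second row. Isolated thrombocytopenia still fails the CR platelet criterion, and nothing excuses that failure unless neutropenia is also present.

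**Step 3: a matched pair.** Both subjects have 3% marrow blasts, platelets 120 and an RBC unit on Day 5, and are assessed on Day 21 (21 − 5 = 16 days after transfusion, under 28).

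- ANC 0.8: CRi.
- ANC 1.5: not CR (transfused within 4 weeks), not CRi (no neutropenia), so MLFS.

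**Step 4: which proportions move.** The second subject fails CR under any reading and would still fail it after the fix, so CR does not change. ORR does not change either, because MLFS and CRi both count under the opening of 4.4.2. Only the split between CRi and MLFS moves.

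**Step 5: scale.** The plan states no figure that depends on this definition. As an illustration, take the 18 expansion subjects (12 + 6, section 4.1.5), all assumed to be in the Full Analysis Set, with exact (Clopper-Pearson) 95% limits:

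- 0/18: lower limit 0; upper limit 1 − 0.025^(1/18) = 0.185.
- 1/18 = 5.6%: lower limit 1 − 0.975^(1/18) = 0.001; upper limit, the 0.975 quantile of beta(2, 17), = 0.273.

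One reassigned subject therefore moves CRi from 0% (0–18.5%) to 5.6% (0.1–27.3%), and MLFS falls by one subject.

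**The case against.** **The waiver may have been meant to stand alone.** The sentence beginning *In addition* can be read that way, and the recently transfused subject with full counts is then CRi. This is a fair reading, although tying the exception to residual neutropenia points the other way. It does not dispose of the point: two programmers could code the same record differently, and untransfused isolated thrombocytopenia is still left out.

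**Efficacy is secondary and descriptive.** There is no response hypothesis, no stopping rule uses CR or CRi, and detailed analyses are deferred to an SAP to be finalized before database lock. This limits the consequences, but it also makes now the cheap time to correct the wording.

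Three stronger inferences are tempting, and the documents do not support them.

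- *That a 4-week RBC-free requirement is itself unworkable because the first response visit comes after 21 days.* Counting back 28 days from Day 21 gives Day −7, but 4.4.2 does not bar the interval from reaching back before Day 1. Cycle 1 is 28 days in cohorts 1 and 2. The end of cycle 3 is study day 63 in cohorts 3–7 (63 − 28 = 35) and day 70 in cohorts 1–2 (70 − 28 = 42), so the interval fits inside the 3-cycle best-response period. Best response is also evaluated over the whole treatment period.
- *That CR is understated.* A recently transfused subject is correctly not CR under the stated definition.
- *That a large share of remissions is lost.* The documents give neither a transfusion rate in subjects with recovered counts nor the number of such subjects. The subjects concerned are scored MLFS and remain responders.

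**Conclusion.** The gap is real on the text of 4.4.2. With <5% blasts and ANC >1, a subject who is recently transfused (platelets ≥100) or has isolated thrombocytopenia (platelets <100) is scored MLFS, while the same subject with ANC ≤1 is scored CRi. The CRi proportion is understated and MLFS overstated. ORR and CR are unaffected. That ORR is unaffected rests on CRi counting towards it, as the opening of 4.4.2 says.

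The size cannot be estimated from the documents; the 0/18 versus 1/18 comparison shows scale only. The recently transfused case depends on the literal reading of the waiver. The untransfused isolated-thrombocytopenia case holds under either reading. This is a moderate issue of endpoint definition that should be corrected before responses are tabulated, and it does not threaten the primary safety objective.

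**What to change.** 1. Reword CRi in 4.4.2 as: all CR criteria except one or more of (a) ANC ≤1 ×10⁹/L, (b) platelets <100 ×10⁹/L, (c) not RBC or platelet transfusion independent. This places all three unclassified rows of the table in CRi.
2. In the Best Response paragraph of 4.4.2, replace the undefined CRp so that the formula agrees with the opening of the section. Make this change together with the first. If the present formula were programmed literally with mutually exclusive categories, a subject moved from MLFS to CRi would drop out of ORR.
3. Reconcile the CR/CRi condition in 4.1.9.3 with the clarified definition, since rewording CRi changes which subjects meet it. How that condition should read is for the sponsor and investigators to decide.
4. Carry the definition into the SAP derivation and apply it to all cohorts alike.

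It would not be sound to go further and upgrade CRi to CR on later blood counts without a new marrow. CR requires marrow findings, and pairing an old marrow with later counts could overstate it.

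The cost is a few lines of wording and some programming. No new data are needed: counts are scheduled, and concomitant therapies, among which Table 8 lists transfusions, are recorded with dates. The downside is that CRi becomes slightly broader.
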